12 Quality Control and Assurance	15
12 References.....	16

A Randomized, Single Blinded Study of the Augmentation of Anterior Cruciate Ligament Reconstruction using Stump-Derived Mesenchymal Stem Cells Versus Standard of Care Anterior Cruciate Ligament Reconstruction

Abbreviations and Definitions

ACL Anterior Cruciate Ligament

AE Adverse Event

AREF Andrews Research and Education Foundation

BTB Bone-Patellar Tendon-Bone

FTA Functional Testing Algorithm

HIPAA Health Insurance Portability and Accountability Act

ICF Informed Consent Form

IRB Institutional Review Board

LDSC Ligament Derived Stem Cell

MRI Magnetic Resonance Imaging

MSC Mesenchymal Stem Cell

PCL Posterior Cruciate Ligament

PI Principal Investigator

PRP Platelet Rich Plasma

SAE Severe Adverse Event

SOC Standard of Care

TDSC Tendon Derived Stem Cell

Tg Transgenic

UP Unanticipated Problem

A Randomized, Single Blinded Study of the Augmentation of Anterior Cruciate Ligament Reconstruction using Stump-Derived Mesenchymal Stem Cells Versus Standard of Care Anterior Cruciate Ligament Reconstruction

1 Background / Scientific Rationale

The anterior cruciate ligament (ACL)'s anatomical importance is to act as a stabilizer of the knee joint during physical activity. This ligament is vitally important during high intensity sports. It is estimated that 250,000 ACL injuries occur in the United States per year (1, 2). Leathers Et. AL. found that patients who elect to undergo ACL reconstruction are at a six times greater risk of tearing the reconstructed graft within the first two years of ACL reconstruction surgery or within their return to sports in comparison to uninjured counterparts (3). This translates to approximately 8.5% of females and 10.5% of males having a tear of the ipsilateral ACL graft within two years of repair or their return to sports. With such high recurrence rates, it is paramount to develop methods to improve outcomes in patients who undergo ACL reconstruction. Bioaugmentation of ACL reconstruction may provide a method to achieve improved outcomes in this patient population.

Orthopedic clinicians and researchers have taken interest in the underlying biology of healing, specifically regarding the application of orthobiologics to improve patient outcomes.

Orthobiologics are a class of therapies that originate from biological products that can be applied at the point of care. Recent studies have focused on using a patient's own tissues to improve current clinical and surgical methods (4, 5). With an increased focus on cell therapy to adjunct current practices, the orthopedic community is determined to develop the least-invasive, convenient, and cost-effective methods to harvest and use stem cells.

Mesenchymal stem cells (MSCs) were first isolated from bone marrow, but they also can be isolated and are contained in synovial tissue, adipose tissue, injured ACL stump tissue, cartilage, and the ACL injury effusion (6-9). MSCs have shown exceptional promise regarding cellular proliferative potential, multipotentiality, and the ability to improve healing in animal models (10-17). In humans, harvesting stem cells from tissues inside the knee joint has recently become a method of interest. Utilizing already available tissues which contain stem cells during arthroscopic knee surgery is particularly beneficial compared to trying to use cells from bone marrow, as bone marrow aspiration for harvest would require patients to undergo a longer duration of anesthesia and positional readjustment over the course of an operation.

During surgery, injury effusion fluid, synovial tissue, and fat tissue found inside the knee are typically removed in order to visualize and repair structures. We recently evaluated this waste tissue in 30 individuals undergoing ACL reconstruction surgery. Culture analysis showed that the knee effusion contained 181 progenitor cells per ml, byproduct tissue contained a concentration of 429 progenitor cells per ml of tissue, and the byproduct fluid contained a

A Randomized, Single Blinded Study of the Augmentation of Anterior Cruciate Ligament Reconstruction using Stump-Derived Mesenchymal Stem Cells Versus Standard of Care Anterior Cruciate Ligament Reconstruction

concentration of 14 cells per ml (14). Animal and human trials are emerging to suggest that autologous augmentation of ACL reconstruction deserves further development (21, 22). We recently completed a study describing the quantity of stem cell available from various waste tissues of ACL surgery: ACL stump, fat pad, bone debris, and cartilage debris. We determined that ACL stump tissue has the most potential to augment ACL reconstruction surgery.

A review of recent studies shows that there is growing evidence in support of bioaugmentation for ACL repairs. Berdis Et. Al. recently published their results for 109 knees in 101 adolescent patients who underwent hamstring ACL reconstruction with bioaugmentation with PRP contained in a porous bovine collagen matrix carrier (23). A total of 132 patients (92%) returned to their preinjury level of competition, while 7 patients sustained a reinjury requiring revision surgery (5%). They concluded that biologic augmentation with hamstring autograft in ACL reconstruction led to a decreased rate of subsequent ACL injury, specifically regarding ACL revision surgery. Patients in this study also showed the ability to return to preinjury level of competition at a faster rate when compared to data from other studies (23, 24).

The desired benefit of MSC therapy is to promote improved bone-to-tendon healing with better biomechanical properties and increased tissue maturity (25). Ligament derived stem cells (LDSC), such as those found in the ACL stump, and tendon derived stem cells (TDSC) have shown better tendon/ligament lineage-specific differentiation when compared to bone marrow counterparts (26). Studies on MSC-based therapies have provided growing evidence that damaged tissues express signaling molecules that act as chemoattractants to aid in the migration, adhesion, and infiltration of MSCs to sites of injury (27). Takeuchi Et. Al. studied the fate of endogenous cells in ACL graft infiltration in transgenic (Tg) pigs. They determined that eventually the endogenous cells proceeded to differentiate into spindle-shaped fibroblast-like cells with a uniform distribution, closely resembling the natural histology of the ACL (28). Nonetheless, future studies tracking MSC differentiation into fibroblasts and other cell types remain necessary.

A key to determining the efficacy of bioaugmentation methods for ACL reconstruction is possessing the ability to accurately evaluate the healing and rehabilitation processes of the patient. Functional testing algorithms (FTA) are used for clinical decision making based on quantitative and qualitative testing and assessment to make clinical judgements to safely return patients back to pre-injury activity and strength. Therapists have developed a systematic guideline and criteria to return to sport based on systematic literature reviews and clinical experience (29). Evaluation with FTA provides the quantitative and qualitative criteria needed to

A Randomized, Single Blinded Study of the Augmentation of Anterior Cruciate Ligament Reconstruction using Stump-Derived Mesenchymal Stem Cells Versus Standard of Care Anterior Cruciate Ligament Reconstruction

make an informed decision on progress towards returning to sports activity. In addition to FTA, magnetic resonance imaging (MRI) is a key analytical method used to provide quantifiable data on the quality of the ACL graft following reconstruction. Evaluation with MRI enables the physician to assess the integrity of the graft, placement within the tunnel, tunnel healing, and healing of the donor site. This information coupled with the functional assessment enables the healthcare team to determine a patient's readiness to return to activity.

2 Objectives

2.1 Primary Objective

The primary objective of this study is to develop a cost-effective, autologous biologic augmentation technique for ACL reconstruction. The technique involves applying tissue harvested with the GraftNet from the patient's ACL stump to an ACL autograft. This study is key to determining a reproducible and effective autologous biologic augmentation technique that can be utilized at the point-of-care during ACL reconstruction surgery.

2.2 Primary Effectiveness Endpoint

FTA results as well as measurements from MRI evaluation will be recorded and utilized to quantify the healing and ACL graft maturation processes. MRI evaluation will be performed in accordance with accepted ACL imaging protocols. This data will then be compared to FTA results and MRI evaluation from patients who did not undergo the bioaugmentation technique for ACL reconstruction.

3 Hypotheses

3.1 Null Hypothesis

H_0 – Participants undergoing the proposed bioaugmentation technique for ACL reconstruction will not have improved healing times and graft maturation as evidenced by functional assessment scores and MRI evaluation when compared to matched participants who only underwent ACL reconstruction without bioaugmentation.

3.2 Alternative Hypothesis

H_1 – Participants undergoing the proposed bioaugmentation technique for ACL reconstruction will have improved healing times and graft maturation as evidenced by functional assessment scores and MRI evaluation when compared to matched participants who only underwent ACL reconstruction without bioaugmentation.

A Randomized, Single Blinded Study of the Augmentation of Anterior Cruciate Ligament Reconstruction using Stump-Derived Mesenchymal Stem Cells Versus Standard of Care Anterior Cruciate Ligament Reconstruction

4 Study Design and Procedures

Study design will be a prospective, single-blinded, randomized, single-center trial. Patients at the Andrews Institute who meet the inclusion criteria will have the study explained in detail and informed consent will be obtained as outlined below. Fifty patients will be blinded, randomized, and undergo an ACL reconstruction surgery. Twenty-Five randomized patients will receive standard of care (SOC) ACL reconstruction surgery. Twenty-Five randomized patients will receive ACL reconstruction surgery augmented with the patient's ACL stump tissue harvested with the GraftNet device (Arthrex, Naples, FL).

4.1 Intraoperative Tissue Harvest and Application

A tissue sample will be harvested from each participant with the GraftNet device (one per surgery) during ACL reconstruction from the ACL stump. During the intra-articular preparation phase of the reconstruction, the tissue sample collected from the ACL stump will be applied to the ACL graft on the back table during the graft preparation phase.

4.2 Post-operative Evaluation and Treatment Plan

Each of the participants will be qualified for the study due to falling within all inclusion criterion and no exclusion criterion. The screening of the inclusion criterion will occur at visit one of the study. Visit one will take place prior to or at the same time as surgery. At this time, the AREF Research Team will review and collect informed consent from each participant. Visit two will occur three (3) months after each participant's ACL reconstruction surgery. At this time, an evaluation by the treating physician will occur along with functional movement assessment and MRI. Visit three will occur six (6) months after each participant's ACL reconstruction surgery. At this time, an evaluation by the treating physician will occur along with functional movement assessment and MRI. Visit four will occur nine (9) months after each participant's ACL reconstruction surgery. At this time, an evaluation by the treating physician will occur along with functional movement assessment and MRI. Visit five will occur twelve (12) months after each participant's ACL reconstruction surgery. At this time, an evaluation by the treating physician will occur along with functional movement assessment and MRI. Visit six will occur eighteen (18) months after each participant's ACL reconstruction surgery. At this time, an evaluation by the treating physician will occur along with functional movement assessment and MRI. Visit seven will occur twenty-four (24) months after each participant's ACL reconstruction surgery. At this time, an evaluation by the treating physician will occur along with functional movement assessment and MRI. At each time point, the treating physician or the therapist performing the functional movement

A Randomized, Single Blinded Study of the Augmentation of Anterior Cruciate Ligament Reconstruction using Stump-Derived Mesenchymal Stem Cells Versus Standard of Care Anterior Cruciate Ligament Reconstruction

assessment can choose to limit the functional movement assessment if there are concerns that the patient may not be ready for the expected load of one or more elements of the functional movement assessment.

At each follow up visit after ACL reconstruction, patient reported outcome measures (PROMs) will be collected by the research team in written or electronic format to assist in assessing the overall health and rehabilitation of each participant. A complete list of PROMs to be collected can be found in section 5.

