4.4 Functional Testing Algorithm

Using the Davies Functional Algorithm (29), the following tests will be performed: Basic Measurements, Sensorimotor System Testing: Balance/Proprioceptive Testing, Closed Kinetic Chain Testing, Open Kinetic Chain Testing, Functional Jump Tests, Functional Hop Tests, Lower Extremity Functional Tests, and Sport-Specific/Position-Specific Testing. Each test will be performed incrementally, and participants will not advance to the next series of tests until the prior assessment has been completed at a satisfactory level. The participants' results from the Functional Testing Algorithm (FTA) and the time required to complete the progression during the rehabilitation period will be quantified and analyzed according to demographic data and pre-injury activity level. The participants will be stratified according to activity level. Participant groups will include general orthopedic patients, recreational athletes, and competitive athletes and will be tested by the FTA accordingly.

5 Patient Reported Outcome Measures (PROMs)

Patient reported outcome measures will be used to quantify physical and psychological aspects of rehabilitation after ACL reconstruction monthly after informed consent has been obtained and surgery has occurred. The patient reported outcomes can be collected in paper format or through the REDCap system. The patient reported outcomes will follow the presented follow up visit schedule: 3months, 6months, 9months, 12months, 18months, and 24months.

A Randomized, Single Blinded Study of the Augmentation of Anterior Cruciate Ligament Reconstruction using Stump-Derived Mesenchymal Stem Cells Versus Standard of Care Anterior Cruciate Ligament Reconstruction

5.1 Tampa Kinesiophobia Scale (TKS):

The fear of reinjury can be a barrier to the rehabilitation of competitive athletes after ACL reconstruction. To quantify the fear associated with reinjury, the Tampa Kinesiophobia (TSK) scale will be provided monthly to participants in the study (31). Kinesiophobia is defined as the fear of movement (31). This measure will be collected to evaluate progression in rehabilitation to take into account not only the physical health of the injured athlete but also the psychological effects and rehabilitation.

5.2 International Knee Documentation Committee Subjective Knee Evaluation Form (IKDC):

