6.2 Participant Eligibility

6.2.1 Inclusion Criteria:

Patients between the ages of 14 and 50 who are scheduled to have ACL reconstruction by one of the investigating physicians will be pre-screened for participation in this study.

6.2.2 Exclusion criteria:

Exclusion criteria will include patients requiring ACL and posterior cruciate ligament (PCL) combined surgery, patients with a history of an autoimmune disease, diabetes, a blood/clotting disorder, or history of previous surgery on the injured knee. Patients will undergo informed consent and an unidentifiable patient study number will be created.

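### The tester's judgement can shape FTA results, which are part of the primary endpoint, yet the protocol names only patients as blinded and does not keep the arm from the FTA tester

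*Protocol*

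**What the plan says.** **Endpoint.** Section 2.2 of the Protocol makes FTA results, together with MRI measurements, the primary effectiveness endpoint and sets out the comparison: "This data will then be compared to FTA results and MRI evaluation from patients who did not undergo the bioaugmentation technique".

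**Who may limit the test.** Section 4.2 schedules a functional assessment at 3, 6, 9, 12, 18 and 24 months. It then gives two people discretion over it: "At each time point, the treating physician or the therapist performing the functional movement" (the sentence continues over a page break) "assessment can choose to limit the functional movement assessment if there are concerns that the patient may not be ready".

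**How a patient advances.** Section 4.4 runs the tests in sequence: "participants will not advance to the next series of tests until the prior assessment has been completed at a satisfactory level". The same section says that the time needed to complete the sequence will be quantified and analysed. It cites a published algorithm for the tests.

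**Who is blinded.** Section 4 says: "Study design will be a prospective, single-blinded, randomized, single-center trial". The only people it names as blinded are the patients: "Fifty patients will be blinded, randomized, and undergo an ACL reconstruction surgery".

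**Who knows the arm.** Under 6.2.1, patients are those "scheduled to have ACL reconstruction by one of the investigating physicians". Under 4.1, the stump tissue "will be applied to the ACL graft on the back table during the graft preparation phase".

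**The concern.** A decision to hold a patient back from a jump or hop test, or to let a patient go on, affects the FTA result recorded at that visit and the time taken to finish the sequence. If the person deciding knows the arm, expectations about the augmented graft can enter the decision without anyone intending it. The bias could run either way. A believer in augmentation might let those patients go on sooner; a cautious clinician might protect the newly treated graft for longer.

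At stake is what an FTA difference between arms would mean. It could reflect healing, or partly who was permitted to attempt a test. The protocol states no concealment from testers and does not say that the reason for limiting a test is recorded. A reader of the results could then struggle to tell the two apart, above all if FTA and MRI disagree. Masking of the tester is a matter of trial conduct, and no later analysis can restore it.

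**Working it through.** The protocol gives no figure on this point, so there is none to reproduce. The check is mainly a reading of the sections together, followed by a small illustration of scale.

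**Step 1. Does judgement enter the primary endpoint?** Yes. Section 2.2 includes FTA results, and 4.2 lets the treating physician or the therapist limit the FTA on concerns about readiness, with no stated criterion. The advance rule in 4.4 sets no threshold in its own text, but the cited algorithm may supply one, so it is not counted here as a second established judgement step.

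**Step 2. Is the tester masked?** Section 4 names patients only. No section names the therapist or treating physician as blinded, calls for an independent assessor, or restricts access to the allocation or the operative record. The protocol does not say that testers are told the arm either.

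**Step 3. Who is known to know the arm?** The operating physician, because the tissue is applied during graft preparation (4.1). If that physician is also the treating physician of 4.2, one of the two people who may limit the FTA knows the arm. This overlap is plausible but not stated.

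**Step 4. Scale that follows from the document.** With 25 patients per arm (Section 4), one patient limited or passed differently moves that arm's pass share at a visit by 1/25 = 4 percentage points.

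**Step 5. Illustration under assumptions.** The protocol names no test and no pass-share endpoint. Assume a comparison of pass shares at one visit, a two-sided Fisher exact test at 5%, 25 per arm, the same true pass share p in both arms, and k would-be passers held back in one arm and none in the other. Let X and Y be independent binomial(25, p) counts. The chance of a false significant result in either direction is the sum of P(X = a) × P(Y = b) over all pairs (a, b) for which the Fisher p-value comparing max(a − k, 0) of 25 with b of 25 is at most 0.05. Exact enumeration gives:

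| p | Expected passers (25p) | k = 0 | k = 2 | k = 5 | 5 held back as share of expected passers |
|---|---|---|---|---|---|
| 0.3 | 7.5 | 2.3% | 6.5% | 33.3% | 5/7.5 = 67% |
| 0.5 | 12.5 | 3.3% | 6.3% | 24.1% | 5/12.5 = 40% |
| 0.7 | 17.5 | 2.3% | 4.7% | 22.0% | 5/17.5 = 29% |

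Two patients leave the rate near the nominal 5%. The 22–33% range needs five would-be passers held back, all in one arm.

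**Step 6. Illustration on completion time.** Assume that mean FTA completion time is compared between arms by a t-test with 48 degrees of freedom. Completion falls at the six visits, with these assumed shares at 3/6/9/12/18/24 months:

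- early: 5/20/35/30/7/3% (SD 4.19 months)
- middle: 2/13/25/30/20/10% (SD 5.45 months)
- late: 0/5/20/30/25/20% (SD 5.69 months)

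Simulation (100,000 trials per case), moving k patients of one arm by one visit, gives a false significant result in 4.9–5.1% of trials for k = 0, 5.1–5.4% for k = 2 and 7.4–8.9% for k = 5. The between-arm comparison of times is inferred from the alternative hypothesis (3.2); 4.4 speaks of analysing time by demographic data and activity level.

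**The case against.** The strongest reply is that this rests on silence. The protocol never says that a therapist knows the arm. The one person shown to know it is the surgeon, which cannot be avoided and fits a declared single-blind design. That stands: a reader might infer that the FTA is tested by unblinded staff, and the document does not establish this. It establishes only that nothing stated prevents it.

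The right to limit a test is a sound safety provision for a healing graft. That also stands, and the fix keeps it.

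Three stronger readings should be resisted.

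- **Advancement as unregulated discretion.** The cited algorithm may set the thresholds, and the Protocol's background section describes it as having quantitative and qualitative criteria.
- **Arm-dependent rehabilitation.** No section says who delivers rehabilitation or whether the trial controls it, so the documents do not support a claim of bias there.
- **Reasons going unrecorded.** The protocol does not state that they are recorded. A case report form could already hold them.

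Nor is the FTA shown to be the only exposed outcome. Section 4.3 includes MRI review of graft integrity and tunnel healing, which can involve reader judgement, and blinding of the MRI readers is not stated either.

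The numbers are modest. With two patients affected, both illustrations stay near 5%, and the largest figure needs two thirds of the expected passers in one arm to be held back.

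What remains is that judgement by the tester enters a primary endpoint in a trial that names only patients as blinded, although the role of the testing therapist already exists and could be masked cheaply.

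**Conclusion.** The concern holds in a limited form. As written, the protocol leaves the FTA tester without stated masking while allowing judgement over part of the primary effectiveness endpoint. It does not show that bias will occur, and its direction and size are unknown. The only scale that follows from the document is 4 percentage points of an arm's pass share per affected patient at a visit. The illustrative error rates rest on an assumed test, assumed pass shares, assumed completion times and one-sided handling of patients. They suggest little effect if two patients are affected. With five, the effect is material for pass share and small for mean time.

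This is a cheap improvement worth making, not a flaw that invalidates the design. The conclusion depends on the absence of any masking statement for testers in the Protocol. If the site already withholds the arm from the FTA therapist, a sentence saying so settles most of it.

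**What to change.** Amend 4.2 and 4.4 to state that:

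1. The arm is not disclosed to the existing therapist who performs the FTA. Referrals and FTA worksheets omit it, and that therapist is not given the operative note where feasible.
2. This masked therapist makes the decisions to limit or advance testing, using the criteria of the cited algorithm.
3. The treating physician keeps a safety override.
4. For every limited test, the reason and the role of the person who decided are recorded, and these are tabulated by arm.

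The log does not mask the physician. It lets a reader see whether overrides fell unevenly between the arms.

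**Cost.** A short amendment, templates without the arm, and fields for the reason and the decision-maker. No extra visits, staff or patients. The downsides are minor administrative effort, and concealment that remains partial if the therapist can read the operative record.
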